### c. Statistical plan including sample size justification and interim data analysis.

As a pilot study, the analyses will likely not have adequate power to detect significant differences. Therefore, effect sizes, rather than statistical significance will be examined for evidence of the effectiveness of the intervention. With a total sample size of 53 we will be able to estimate the effect size associated with the intervention. This effect size will be compared to the literature for similar interventions and used to estimate the needed sample size to a fully powered effectiveness trial. There will be no interim data analysis.

Understanding the factors that predict which intervention components are successfully implemented and for which participant subgroups will be critical for fine-tuning this multicomponent intervention for future proposals that will extend efficacy examinations and effect modification analyses. Acceptability of the intervention will be examined in multiple ways. We will examine percentages of people who stayed in each arm of the study and conduct numerous descriptive correlational analyses of the association between

the intervention compliance and other variables. These analyses will quantify intervention implementation by demographic and participant health variables. Analyses that utilize the post-randomization data (e.g. treatment compliance) will be evaluated in supplementary analyses. We will distinguish non-compliance with intervention from attrition or loss to follow-up, i.e. missing data. We will also use the participant satisfaction data to examine acceptability of the intervention.

d. Early stopping rules.

As this is a low-risk behavioral intervention pilot, we have not defined any early stopping rules.

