### 2. Objectives

Aim 1: Test the feasibility and gauge an initial effect size of the intervention to improve QOL (primary outcome), fatigue and caregiver burden (secondary outcomes) among family caregivers from baseline to 16 weeks.

Aim 2: Test whether fatigue and caregiver burden are associated with a physiological measure of resilience, inflammatory cytokines (IL-6 and IL-10) detected in sweat patches and a self-reported measure of resilience, controlling for covariates.

Aim 3: Evaluate changes in heart rate variability (HRV), an indicator of physiologic stress, pre- and post-intervention.

Aim 4: Describe care recipient 6-month palliative care utilization, all-cause hospitalization, and mortality, comparing intervention and control.

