## 4. Study Procedures

**Figure 2: Flowchart of Study Design**

control groups are used to first provide an untreated comparison and second to allow wait-listed participants an opportunity to receive the intervention at a later date. This is especially appropriate given that very few services are currently offered to HF caregivers. To account for estimated 20% attrition we will recruit 53 participants.

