### **Johns Hopkins Bayview Clinic Recruitment:**

We will distribute a recruitment flyer in the heart failure clinic at the Johns Hopkins Bayview Medical Center. Caregivers that respond to the recruitment flyer will be screened for eligibility. If they are eligible, we will contact them by phone to explain study procedures. If interested in participating, we will schedule the caregiver's baseline interview within 10 days of initial contact. During the baseline interview the research assistant will re-explain the study, obtain written consent (if interview is in-person), or e-consent (if the interview is by phone or DoxyMe or Zoom video call).

**Overview of Study Design (Figure 2):** We propose an open label pilot (n=5) with a subsequent single-blind, two group randomized pilot trial to test the feasibility and gauge an initial effect size of the Caregiver-Support intervention to improve QOL. The immediate intervention group (n=20) will receive the intervention during weeks 0-16. The waitlist control group (n=20) will be provided written materials with community resources for caregivers during the first 16 weeks, then they will begin the intervention. Waitlist

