## 7. Study Statistics

Exploratory and descriptive analysis will be completed for all study variables. Variables will be examined for normality and examined with means and standard deviations or medians and interquartile ranges accordingly. Baseline characteristics comparing the two groups (waitlist vs. immediate intervention) will be assessed. Any differences between the groups will be adjusted for further analysis. The significance level will be set at 0.05. Sensitivity analyses will be conducted adjusting for variables on which the group differ and compared to the pattern of results in the main analyses.

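### Section 7.c sizes the full trial on the pilot's observed effect size, which with about 20 caregivers per arm is too imprecise for that use

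*Combined protocol and SAP*

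**What the plan says.** Aim 1 (section 2) sets out to test feasibility and to "gauge an initial effect size of the intervention to improve QOL". Section 7.c concedes that power is likely to be inadequate and says that instead "effect sizes, rather than statistical significance will be examined for evidence of the effectiveness of the intervention". It then gives the estimate a use in design: after a comparison with published results for similar programmes, it is to be "used to estimate the needed sample size to a fully powered effectiveness trial".

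Section 7.a names Hedges' g for the between-group difference in change. It adds a second comparison, with clinically significant improvement reported in the literature, but gives no value for that improvement.

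On numbers, the Overview of Study Design in section 4 states: "The immediate intervention group (n=20) will receive the intervention during weeks 0-16" and "The waitlist control group (n=20) will be provided written materials with community resources for caregivers during the first 16 weeks". The same section says: "To account for estimated 20% attrition we will recruit 53 participants". Section 7 adds: "The significance level will be set at 0.05"; it does not say whether this is one- or two-sided.

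The plan states no confidence interval for g, no shrinkage or lower-bound rule, no target difference for sizing, no action if g is near or below zero, and no criterion for going on to the full trial.

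**The concern.** An effect estimated on about 20 people per arm carries an error that can be as large as a small or moderate effect. The sample-size formula divides by the square of that estimate. A moderate overestimate therefore gives a trial far too small, and a moderate underestimate gives one far too large to run. Looking at effect sizes in place of p-values does not reduce this error. Hedges' correction removes the small-sample bias of Cohen's d but leaves the sampling error as it was.

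At stake is the next trial: it could be described as fully powered and have well under its nominal power. Sizing that trial is the use that section 7.c gives to the estimate. This would remain even with a single QOL score, an agreed SD and the correct number analysed.

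**Working it through.** **The plan's own figure.** The formula behind 53 is not stated. Adding 20% to the 40 randomised and then the 5 open-label participants gives it exactly: 40 × 1.2 + 5 = 53. Dividing by the retained fraction gives 40/0.8 + 5 = 55.

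**Analysable number per arm.** If 48 are randomised and 20% are lost, 48 × 0.8 = 38.4, about 19 per arm. If all 53 were randomised, 53 × 0.8 = 42.4, about 21 per arm. The range is 19 to 21, around the planned 20. The open-label participants have no control group and cannot contribute to a between-group g.

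**Assumptions, because the documents give no value.** True standardised effect d = 0.2, 0.3, 0.4, 0.5 or 0.8; nominal power 80% for the full trial; two-sided 0.05; equal arms.

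**Precision of g.** SE(g) = √(2/n + d²/(4n)). With n = 20 and d = 0.4: √(0.100 + 0.002) = 0.319, so the 95% interval is ±1.96 × 0.319 = ±0.63. With 19 and 21 per arm it is ±0.64 and ±0.61.

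**Size implied by g.** n per arm = 2(1.960 + 0.842)²/g² = 15.70/g². If the true effect is 0.4, 99 per arm are needed.
- Pilot one SE too high: g = 0.72, so 31 per arm. True power is Φ(0.4 × √(31/2) − 1.96) = Φ(−0.385) = 35%.
- Pilot one SE too low: g = 0.081, so about 2,400 per arm.
- Chance that g is zero or negative, so that no usable size results: Φ(−0.4/√(2/20)) = Φ(−1.265) = 10%.

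**Simulation.** Pilots with 20 per arm were simulated, g was computed with the small-sample correction, the full trial was sized from g, and its power was evaluated at the true d. Results are for pilots with g > 0.

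| True d | n per arm needed | Median true power | Chance that true power is below 50% |
|---|---|---|---|
| 0.2 | 393 | 46% | 53% |
| 0.3 | 175 | 64% | 40% |
| 0.4 | 99 | 73% | 32% |
| 0.5 | 63 | 77% | 26% |
| 0.8 | 25 | 81% | 15% |

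At d = 0.4 the planned size runs from 23 to 1,034 per arm (10th to 90th percentile). With 19 or 21 per arm the results move by about one point.

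**Nominal power of 90% instead.** At d = 0.4 the median true power is 85%, and it is below 50% in 23% of cases.

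**If the full trial follows only a favourable g.** The plan has no such rule, so these cut-offs are assumptions. At d = 0.4 with 20 per arm, mean true power is 69% for any g > 0, and 66%, 62%, 55% and 46% for cut-offs of 0.1, 0.2, 0.3 and 0.4.

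**The case against.** **The effect size is not the only input.** Section 7.c also compares it with similar interventions, and section 7.a with clinically significant improvement. This stands in part: a reader might infer that g alone mechanically fixes the next sample size, and the text does not go that far. But neither comparison comes with a rule for changing the estimate, and the pilot effect remains the quantity named for sizing.

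**Attrition is already covered.** This stands. A reader might take 20% off 20 and work with 16 per arm, but recruitment is raised to 53 to offset the loss. The figures above therefore use 19 to 21.

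**Selection after a good result is conjecture.** This stands as a caution. It is tempting to say that the effect carried forward will be inflated because only promising pilots lead to trials. The documents contain no progression rule, and the loss of power depends strongly on the cut-off assumed. The main result conditions only on g > 0.

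**The rule often works.** At d = 0.4, 45% of the trials sized in this way would have at least 80% power, and at d = 0.8 the median is 81%. That is true, but the plan offers no basis for expecting an effect that large.

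**It concerns another trial.** The sentence changes nothing in randomisation, data collection, the GEE model or safety, and the pilot has other aims. This limits the severity. It does not remove the point, because the plan itself assigns this use to the estimate.

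**Conclusion.** The concern holds in this form: with about 20 analysable caregivers per arm, the observed g is an unreliable basis for the full trial's sample size, and section 7.c contains no safeguard. For true effects of 0.2 to 0.5 SD, between 26% and 53% of trials sized on a positive g would have less than 50% power against a nominal 80%. At 0.8 SD the figure is 15%. These results rest on the assumed true effects, 80% nominal power and two-sided testing; the conclusion is the same for 19 to 21 per arm.

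A reader might go further and call the pilot's own comparison invalid. Nothing in the documents supports that, since the analysis of this study does not depend on the sentence. The change should be made, but the conduct of the pilot does not depend on it.

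**What to change.** Replace the sizing sentence in section 7.c with text to this effect:

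> *The full trial will be sized on a target difference in the primary QOL score, chosen and justified by the sponsor and recorded before unmasking. The pilot will supply the SD, the baseline to week-16 correlation and attrition, with an allowance for imprecision in the SD. Hedges' g will be reported with its 95% confidence interval as a descriptive result. It will not be treated as evidence of benefit and will not determine the sample size.*

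The clinically significant improvement that section 7.a already mentions is the natural source for the target. The documents give no value, so the sponsor must state and defend one, for one named QOL score. The allowance for the SD can be an upper confidence limit. As one example among several conventions, the one-sided 80% limit with 38 degrees of freedom is 1.12 times the pilot SD, which raises the sample size by about 25% (1.12² = 1.25).

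The cost is a change of wording and a short justification of the target; no extra data are needed. The downside is that the full trial may be larger than a favourable pilot g would suggest.

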## 8. Risks

Minimal risks to study participants are expected. Some participants may experience some discomfort or fatigue in study interactions or in answering questions about their caregiving. Interviewers and interventionists will be trained to handle these minimal discomforts if they should occur, offering opportunities to rest throughout the interviews and intervention sessions.

**Education in protection of human research participants:** All investigators have completed the Johns Hopkins University School of Medicine Research Compliance course and have been certified to conduct human research. The course consists of the University of Minnesota Web modules on Informed Consent, the consent Process, and After Informed Consent, Johns Hopkins University School of Medicine module on local IRB requirements, and achievement of a passing score on the Johns Hopkins Knowledge Assessment module. According to the policies of the Johns Hopkins University, approval for this research will be obtained from the IRB office for research using human subjects prior to collecting data. Minorities and women are included in this study, and all data will be presented in group format. Participants will be assigned a code number on initial entry and all subsequent questionnaires will be identified only by code number. Information needed for follow-up contact (names and addresses) will be kept separately from all other data.

**Procedures for protecting against and minimizing potential risks:** The interviewer will notify the Principal Investigator (a nurse) of any concerns for distress related to the study and participants will receive a follow-up telephone call to assure that the mild distress has resolved. In situations where there is initial severe distress or when the distress has not been resolved, we will consult with our Co-Investigator, [name], FNP-BC. Furthermore, if any physical problems emerge during any of the study for either patients or caregivers, immediate medical attention will be sought for the participant. The research assistants will all be nurses and will be trained to call 911 if they have serious concerns of an emergent issue.

The risk of invasion of privacy will be addressed with participants during the informed consent process. All personnel involved in the study will be fully trained and certified in the protection of human subjects and HIPAA regulations. This certification will be kept current throughout the study. As part of the informed consent process, participants will be notified of their rights pertaining to protected health information. Participants will be informed that they can stop the questionnaire and rest at any time. All study participants will be provided referral information to existing health services as in typical or usual care. Thus, participants have the information to access any services that they may perceive as necessary independent of their study participation.

The risk of breaching study participant confidentiality will be minimized by identifying all participants by code numbers and securing all data collected in locked files in the PI's office and screening information to locked file cabinets with limited staff access. Pre-coded data collection instruments are prepared for use with study participants at each testing occasion. Identification numbers to assure subject confidentiality will be used. Only one master log of subject name, address and telephone number and study identification assignment will be maintained on site in the locked PI's office. This log, in both hard copy and electronic

file saved to an encrypted USB drive, will be stored in a locked filing cabinet separate from other identifying information. All completed data collection instruments are stored in locked filing cabinets. Audio recording of screens, interviews, and intervention will be identified by numbers only and stored on the Johns Hopkins Secure Analytic Framework Environment (SAFE) virtual desktop of [name] who will provide fidelity oversight of the interventionists. Access to these computer files will be password protected, audio recordings will not contain respondent name or other personal identifying information. Recorded interviews and key stakeholder meetings will be transcribed by a transcription service. All recordings and transcripts will be password protected and stored on the Johns Hopkins SAFE virtual desktop. Each transcript will be redacted for identifiers prior to analysis. Audio recordings from intervention sessions will be used only for quality control and training purposes and then destroyed (deleted from computers) within one year of trial completion. We will use either DoxyMe or Zoom. DoxyMe is encrypted, collects no protected health information (PHI) and any data transmitted during the call is destroyed when the call ends. It is both HIPAA and HITECH compliant (<https://doxy.me/en/about/>). We have created a HIPAA compliant Zoom account through the Johns Hopkins School of Nursing IT department dedicated to this research study and it will only be used for study participant virtual visits and will only be available to the study team.

**Data Safety and Monitoring:** The PROMOTE Center will have a standing DSMB to review this pilot study. The Center will provide for collection and storage of data across pilot studies. These data will be de-identified and stored in databases on the Johns Hopkins Secure Analytic Framework Environment (SAFE) virtual desktop. Data will be restricted to those with permission to access it. Investigators will use the REDCAP data entry system. However, any paper copies of consents or other study data will be stored in locked file cabinets.

The DSMB will be responsible for reviewing the safety of study participants during the conduct of this study and provide recommendations to the research team on specific aspects of the research protocol as it pertains to safety, potential study alerts and adverse events. Specific responsibilities of the DSMB will be to: a) provide an independent periodic review of recruitment and enrollment progress; b) review adverse events (AEs) including serious events and offer recommendations regarding the trial based on such observed events; c) serve in a consultative capacity to the research team regarding study procedures to address ethical dilemmas (e.g., reporting of abuse), safety of subjects in the trial, and appropriateness of all study procedures. We will not conduct interim analyses for this pilot study.

**Recruitment, Adverse Events (AE) and Alert Reports:** Reports presented to the DSMB will include data on enrollment (study accrual by month; comparison of expected to actual enrollment; number of individuals screened, number eligible and number ineligible, number randomized by gender), AEs, and alerts. Also, the DSMB will receive reports of the number of study participants who discontinue from the treatment group and/or the study and reasons for discontinuation. We propose that reports be provided to the DSMB twice yearly. However, the DSMB will decide upon the schedule of reports at their first organizational meeting. Also, the DSMB may request reports as needed as well as the unmasking of the data should they deem this necessary. If unmasked efficacy data is required, the biostatistician for this study ([name]) will serve as a liaison between the PI, database and the DSMB in order to assure that the PI and investigative team remains masked. For the first meeting of the DSMB, members will receive and review the following materials: a) Grant proposal, relevant appendices, reviewers' comments; b) Standard Quality control procedures (see Facilities/Resources); c) IRB approved consent forms; d) Baseline and follow-up batteries; e) Shell of data base for management of interview schedules and enrollment information; f) Subject tracking forms; g) Alerts and Adverse event procedures and forms; h) Intervention treatment documentation forms; i) Shell for reporting recruitment and enrollment; j) Data shells for reporting tracking information and baseline characteristics; k) Decision rules for intervention termination (e.g., death, extended hospitalization, relocation);

**Adverse Event (AE) Reporting:** The DSMB is notified by the principal investigator of any serious AE within 48 hours of initial notification to the project team. All members of the DSMB will receive copies of all safety reports at the time of submission to the IRB of JHU. In addition, a listing of all AEs and their attribution (e.g., study related, intervention related, or unrelated to study or treatment) will be provided to the DSMB on a monthly basis. We do not anticipate any adverse reactions to the intervention. Based on our previous work and studies in this area by others, there is only a small risk that participants will become increasingly anxious as a consequence of the intervention and being involved in an active problem-solving, behavioral activation approach. However, interventionists will be well trained to manage this reaction or make an effective referral if necessary. Given that both data collection and interventions may occur in people's homes, there is the potential for a member of our research team to encounter a potential emergency situation that is not related to study participation (e.g., dehydration, environmental risk, medical emergency). We refer to such events as alerts and have well developed procedures for their management. All alerts are reported to the DSMB on a biannual basis. However, the reporting of alerts to the IRB of JHU is not required (see Chart below of potential alert events and plan for their management and reporting).

**Plan for reporting unanticipated problems or study deviations:** There are only minimal risks associated with the trial. It is anticipated that participants will experience more benefits than risks from their participation in the trial.

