Participants will be randomized to receive either the immediate intervention group or the waitlist control group. In the waitlist control group, participants will receive usual care for the first 16 weeks (which is limited to printed materials provided in the clinic) and then begin the intervention. The intervention will consist of 5 in-home sessions with a nurse interventionist. Each participant will receive each intervention component but interventionists will systematically tailor content to the participants' goals based on protocols. All participants will be reassessed at 16 weeks and 32 weeks by a research assistant (RA) masked to treatment condition. The primary outcome will be improvement in quality of life between baseline and 16 weeks. Other endpoints include group differences in fatigue, caregiver burden, self-reported and physiological measures of resilience up through 32 weeks after the intervention. We will also examine the acceptability of the intervention using intervention compliance and participant satisfaction data.

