## **Open Label Phase:**

The first five participants will be enrolled into an open label pilot study, in which they will automatically receive the Caregiver-Support intervention. The participants will be interviewed after program completion to get feedback on the data collection instruments, intervention content including the number of visits and user-friendliness of intervention components (e.g. purpose in life activity), and satisfaction with the overall program process. This feedback will be used to modify the Caregiver-Support intervention for the waitlist control trial that will begin enrollment following the open label phase.

**Randomization:** Within 48 hours of the baseline interview, we will randomize using redcap randomization and communicate the assignment to participants by letter. At that same time, we will inform the nurse interventionist of the new participant. The intervention nurse will contact the participant within one week to schedule the first appointment. The waitlisted group will receive usual care for caregivers for the first 16 weeks, which is normally limited to inclusion in some clinical assessment and teaching during patient visits. Waitlisted participants will receive monthly study postcards to encourage retention. After 16 weeks, they will begin the intervention. The 32- week assessment will measure whether immediate intervention participants continue the strategies on their own and whether they continue to improve on the self-report scales and will measure improvement following the intervention for waitlisted participants.

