**Table 3: Study Visit Timeline for Immediate Intervention Group\***

Format and timing of visits	Key activities
Baseline Data Collection	Sweatpatch application Heartrate Variability Measurement Survey
Sweatpatch Pickup	72 hours post-application, remove sweatpatch and deliver for storage and analysis
Randomization	Mail randomization results
Home Visit Week 1	Assessment Set goals and discuss priorities Remove sweatpatch and deliver for storage and analysis (if not already performed)
Home Visit Week 3	Purpose in Life activity Instrumental Support activity: Benefits Check Up Assess goal attainment and revisit strategies
Phone Check-in Week 4	Review/edit purpose statement Assess goal attainment and strategies to achieve goal
Home Visit Week 6	Social Support Activity Assess goal attainment and strategies to achieve goal Follow-up re: instrumental support
Phone Check-in Week 8	Review/edit purpose statement Assess goal attainment and strategies to achieve goal
Home Visit Week 10	Assess goal attainment and strategies to achieve goal Follow-up re: instrumental and social support
Phone Check-in Week 12	Review/edit purpose statement Assess goal attainment and strategies to achieve goal
Home Visit Week 14	Review of progress, goals and purpose Discuss how caregiver will involve social support in next goals
Data Collection Visit Week 16	Sweatpatch application Heartrate Variability Measurement Survey
Sweatpatch Pickup	72 hours post application
Data Collection Visit Week 32	Sweatpatch application Heartrate Variability Measurement Survey
Sweatpatch Pickup	72 hours post application

\* Waitlist control group will begin intervention at week 16.

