#### Data Management:

Data from screening, intervention sessions, and final data collection will be entered onto forms that the data manager will check for completeness and appropriateness. The data manager will send reports of missing or inappropriate entries to the PI every week for clarification and resolution. As a phase 1 pilot study, a Data Safety and Monitoring Board is not required, however, as part of the P30 PROMOTE Center, a Data Safety and Monitoring Board has been established. Details are provided in the human subjects section.

Fidelity: The fidelity plan is based on the NIH Behavior Change consortium developed by national leaders. We will enhance fidelity through design elements (intervention is distinct and based on theory), training (using an intervention manual), delivery (reminder calls the night before intervention sessions, and measure fidelity through records of home sessions (by date and duration), checklists completed by study team

members and direct observations and discussions concerning intervention engagement to evaluate receipt, and enactment. Ten percent of sessions will be audio taped which will be reviewed by the research coordinator using a priori monitoring checklists developed for this pilot trial. All data collection and intervention interactions will be recorded. Evaluation will include periodic assessments of data quality, participant recruitment, accrual, and retention. Feedback will be provided to each interventionist who will provide case presentations in supervisory sessions. Bi-weekly meetings of the nurse interventionist with the Research Coordinator, the PI, and [name] will assure on-going fidelity to the intervention.

**Study duration and number of study visits required of research participants:** Participation in the study will consist of initial study consent, baseline, 16 and 32-week data collection and 5 study interactions for the intervention. Based on participant preference, the nurse interventionist may also arrange phone calls between visits to assess progress towards goals.

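### The protocol sets out AE reporting but no common AE ascertainment schedule, and staff contact differs by arm in weeks 1-14, so AE counts are at risk of detection bias

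*Combined protocol and SAP*

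**What the plan says.** **Reporting.** Section 8, under Adverse Event (AE) Reporting, states that "a listing of all AEs and their attribution (e.g., study related, intervention related, or unrelated to study or treatment) will be provided to the DSMB" monthly. Serious AEs go to the DSMB within 48 hours of the project team first being notified; no source of that notification is named. The DSMB may make recommendations about the trial from observed events and may ask for unmasking.

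**Ascertainment.** No section defines an AE, schedules an AE question or sets a collection window. Table 3 describes the week 16 and week 32 visits as sweat patch application, then "Heartrate Variability Measurement Survey" (two entries run together). Table 4, the list of instruments, has no AE or health-event item for the caregiver. The routes described in Section 8 are an interviewer noticing distress, an interventionist managing anxiety, and staff encountering an emergency at home or by phone.

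**Contact in the immediate arm.** The Abstract states: "The intervention will consist of 5 in-home sessions with a nurse interventionist". Table 3 runs from a week 1 visit to "Home Visit Week 14", with calls in between, the last being "Phone Check-in Week 12". The study-duration paragraph under Data Management makes the calls optional: "Based on participant preference, the nurse interventionist may also arrange phone calls between visits to assess progress towards goals". The fidelity paragraph adds "reminder calls the night before intervention sessions".

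**Contact in the waitlist arm.** For the first 16 weeks this arm has usual care and written materials. The Randomization paragraph adds: "Waitlisted participants will receive monthly study postcards to encourage retention".

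**The concern.** Where no one is asked about AEs on a schedule, an event tends to enter the record when the participant volunteers it or a staff member is there to notice it. Staff presence differs by arm throughout the period in which one arm is untreated. With equal true event rates, the arm being visited could show more events.

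Two uses of the record are exposed. First, if the DSMB looks at events by arm, weeks 0-16 are the only randomized comparison with an untreated group, and that is where contact is least balanced. Second, attribution to the intervention is harder to judge when events are noticed mostly during intervention contacts. The pilot is meant to inform a larger trial, so a safety record that cannot be compared between arms loses some of its value.

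**Working it through.** **1. The plan's own count.** Home visits in Table 3 fall at weeks 1, 3, 6, 10 and 14, which makes 5. This matches the five sessions in the Abstract.

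**2. Calls.** Table 3 lists calls at weeks 4, 8 and 12, which makes 3. Because they depend on participant preference, a participant has 0 to 3. Nurse contacts in weeks 1-14 are therefore 5 + 0 = 5 to 5 + 3 = 8. One reminder call before each of the five sessions would bring the maximum number of staff contacts to 8 + 5 = 13.

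**3. Waitlist arm, same weeks.** There are no scheduled staff contacts once the baseline procedures, including patch removal at 72 hours, are complete. Postcards number about 16/4 = 4 and go one way.

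**4. Contacts in both arms.** Adding the week 16 assessment gives 6 to 9 against 1. No AE question is listed for that assessment.

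**5. After week 16.** If the Table 3 schedule is shifted by 16 weeks (an assumption; only the starting week is given), the waitlist arm has visits at weeks 17, 19, 22, 26 and 30 and calls at weeks 20, 24 and 28. The immediate arm then has only the week 32 assessment.

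**6. Can the bias be sized?** Only under assumptions, because the documents give neither a self-report rate nor a recall rate. Let the true AE rate be equal in both arms and let s be the share of events that participants report unprompted.

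*Week 16 does not ask about AEs.* If nurse contacts capture a share q of the remaining events, the recorded ratio (immediate to waitlist) is [s + (1 - s)q]/s.
- s = 0.10: 5.5 (q = 0.5) to 9.1 (q = 0.9)
- s = 0.25: 2.5 to 3.7
- s = 0.50: 1.5 to 1.9
- s = 1: 1.0

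*Week 16 does ask, and nurse-detected events are pooled with the answers.* Let events be uniform over 16 weeks, with those not volunteered captured at the next contact and recall halving every h weeks. A gap of L weeks between contacts contributes (h/ln 2)(1 - 0.5^(L/h)) to the captured time. For s = 0 and h = 4:
- Waitlist, one gap of 16 weeks: 5.77 x (1 - 1/16)/16 = 0.338
- Immediate, eight contacts plus week 16 (two gaps of 1 week, seven of 2 weeks): 5.77 x [2(1 - 0.5^0.25) + 7(1 - 0.5^0.5)]/16 = 0.854
- Ratio: 0.854/0.338 = 2.5 (2.3 if only the five visits take place)

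With s = 0 and eight contacts, the ratio is 4.1 at h = 2, 1.7 at h = 8 and 1.0 with perfect recall. With s = 0.5, it is 1.5, 1.4, 1.25 and 1.0 for h = 2, 4, 8 and perfect recall.

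Across these assumptions the ratio runs from 1.0 to about 9. The direction is consistent, but the size is not determined.

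**The case against.** A reader might infer that AEs surface *only* through staff contact. The documents do not say so. The serious AE clock starts when the team is notified, from any source, so self-report and family report are not excluded. Section 8 also lists alert and AE procedures and forms, and the baseline and follow-up batteries, among the DSMB materials. Their content is not shown, and they may include elicitation questions. What stands is narrower: the protocol text sets no common schedule.

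A reader might also infer that the AE comparison *is* biased. No by-arm AE analysis is planned: Section 7 has none, there are no interim analyses or stopping rules, and the DSMB receives a listing with individual attribution, which includes an unrelated category. Unrelated emergencies that staff encounter are handled separately as alerts. But the DSMB can ask for unmasking, so a comparison by arm remains possible.

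A third inference would be that weeks 0-16 cannot show whether the intervention raises distress. That is wrong. Both arms complete the PHQ-8, the SF-36 with its affective well-being scale, and the strain and coping scales at baseline and week 16, with masked assessors. The interviewer's duty to report distress also applies in both arms. None of these is an anxiety scale, although increased anxiety is the one intervention risk that Section 8 names. Nor do they record falls, injuries or admissions of the caregiver, and they are not linked to AE reporting.

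Finally, this is a minimal-risk pilot with 20 per arm, where one participant is 1/20 = 5 percentage points. No AE comparison will be precise, whatever the method. That limits how much is at stake, but it is no reason to collect the events unevenly.

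**Conclusion.** The point holds as a risk of detection bias. Reporting is specified, common ascertainment is not, and scheduled nurse contact in weeks 1-14 is 5 to 8 in the immediate arm against none in the waitlist arm, with the imbalance reversing after week 16. A flat 8 against 0 would overlook that three of the contacts are optional and that both arms share the week 16 assessment.

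The contact counts come directly from the protocol. The size of any bias does not: it depends on self-report, nurse capture and recall, and the ratios above only show how widely the answer moves with those assumptions. The conclusion also assumes that the AE forms not shown do not already set a common schedule of questions. The point does not touch the quality-of-life analysis. It is an inexpensive improvement to the safety record.

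**What to change.** Add the same few health-event questions to the existing week 16 and week 32 surveys in both arms, covering the time since the last interview: emergency visit, hospital admission, fall or injury, new or worse distress, and skin reaction to the patch. Word them neutrally, with no mention of visits or the nurse.

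State in Section 8 that any by-arm AE summary uses these answers only, and that events found at intervention visits or calls are listed separately with their detection source. This separation is essential: step 6 shows that asking at week 16 and then pooling nurse-detected events restores balance only with perfect recall or complete self-report. With the summary limited to the common questions, equal true rates give an expected ratio of 1.0, provided recall is similar in the two arms. Serious AE reporting stays unchanged. If the existing AE forms already contain such questions, it is enough to state their timing and use in the protocol.

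The cost is about five REDCap items at visits that already take place, and no extra staff. The downsides are a few minutes per interview, recall over 16 weeks, and a slight risk that an answer reveals the allocation, which the wording limits. Asking these questions after the outcome instruments would reduce that risk further.
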